9.6.8 Antibody Formation

The incidence and percentage of subjects who develop anti-AMG 330 antibodies (binding) at any time by cohorts and indication (Group1, Group2, Group3) will be tabulated. Positive anti-AMG 330 antibody data will be listed and reviewed for each subject. The impact of immunogenicity on safety may be explored by assessing adverse events and serious adverse events.

9.6.9 Exposure to Investigational Product

Details of AMG 330 administration will be listed for every subject for DLRM. In primary and final analyses, a listing of the unique manufacturing lot numbers, and a listing of the subjects administered each manufacturing lot number will be provided. Descriptive statistics will be produced to describe the number of cycles initiated, completed and discontinued, the duration of therapy and the cumulative dose will be produced to describe the exposure to investigational product by groups and dose cohorts separately.

9.6.10 Exposure to Concomitant Medication

All medication will be coded using the WHO drug dictionary. A subject listing of all concomitant medications will be presented for DLRM. In the interim, primary and final analyses, the number and proportion of subjects receiving concomitant medications will be summarized by preferred term for each treatment group and indication as coded by the World Health Organization Drug (WHO DRUG) dictionary.

9.7 Other Analyses

9.7.1 Analyses of Pharmacokinetic or Pharmacokinetic/Pharmacodynamic Endpoints

For AMG 330, pharmacokinetic parameters (half-life, steady-state concentration, volume of distribution, and clearance) will be determined from the time-concentration profile using standard non-compartmental approaches and considering the profile over the complete sampling interval. Based on the review of the data, analyses to describe the relationship between AMG 330 exposure and either pharmacodynamic effect and/or clinical outcome may also be performed.

Serum concentrations of AMG 330 will be determined using a validated assay. Parameters to characterize cellular kinetics related to cell expansion (eg, C_{max} , T_{max} and partial AUC) and cell persistence (eg, $T_{1/2}$, T_{last} and C_{last}) in PBMCs, parameters will be estimated using standard non-compartmental approaches and summarized by dose level using means, standard deviations, medians, minimums, and maximums.

Serum concentrations below the lower limit of quantifications will be set to zero for the estimation of the cellular kinetic for each subject and for the calculation of the summary statistic for each time point. Actual dosing and sampling time will be used for all calculations. The reasons for excluding any sample from the analyses will be provided.

Individual concentration-time data will be summarized by dose level. Individual concentration-time data will also be tabulated and presented graphically. Summary statistics will be computed for each sampling time and parameter as appropriate. Additional Cellular kinetic analyses, including but not limited to analysis of the relationship between AMG 330 dose and exposure parameters (AUC and Cmax) and dose proportionality assessments, may also be conducted. Based on the review of the data, analyses to describe the relationship between AMG 330 exposure and either Pharmacodynamic effect and/or clinical outcome may also be performed.

A preliminary assessment of dose proportionality will be made using the Power Model Statistical analysis of $AUC_{(0-t)}$ and Cmax of AMG 330 will be performed after log transformation of the data. The Power Model:

$$Y = \alpha \text{ dose}^\beta$$

where Y is the pharmacokinetic parameter and α is an intercept term. This becomes a linear relationship following a logarithmic transformation, to which a linear regression approach can be applied as,

$$\log(Y) = \beta \times \log(\text{dose}) + \log(\alpha)$$

The coefficient of the slope with 90% confidence intervals, on the log scale, will be calculated.

Descriptive statistics will be provided for biomarker data by dose, dose schedule, and time as appropriate.

9.7.2 Analyses of Clinical Outcome Assessments

NA

9.7.3 Analyses of Health Economic Endpoints

NA

9.7.4 Analyses of Biomarker Endpoints

Biomarker data may be incorporated in additional exploratory subgroup or multivariate analyses. The analyses of biomarkers will be considered exploratory and may be performed after collection of all samples during the conduct of the study and therefore may

be reported after the primary analysis. Changes in expression or expansion level of biomarkers and their relationship to dose may be evaluated. Summary statistics over time may be provided and graphical presentations may be used. Details of analysis will be provided in Contributing Scientific Report for exploratory biomarker analysis.

10. Changes From Protocol-specified Analyses

- The following inclusions in the SAP are in anticipation of incorporation in Protocol Amendment 10:
 - event-free survival endpoints replacing time to progression in R/R AML and MDS groups to address relapse/refractory AML subjects who are already in a progressive state and never respond.
 - removal of duration of response endpoint for MRD+ AML group
 - overall survival for all groups in the expansion cohort
 - Treatment-emergent definition accounts for long-term follow-up by defining events as treatment-emergent by looking up to the earlier of 30 days after last dose of AMG 330 or end of study date.
 - Summary of adverse events amongst subjects who take siltuximab.

11. Literature Citations / References

12. Prioritization of Analyses

NA

13. Data Not Covered by This Plan

NA

14. Appendices

Appendix A. Handling of Dates, Incomplete Dates and Missing Dates

Imputation Rules for Partial or Missing Dates for Adverse Events and Concomitant Medications

Start Date		Stop Date						
		Complete: yyyymmdd		Partial: yyyymm		Partial: yyyy		Missing
		< 1 st dose	≥ 1 st dose	< 1 st dose yyyymm	≥ 1 st dose yyyymm	< 1 st dose yyyy	≥ 1 st dose yyyy	
Partial: yyyymm	= 1 st dose yyyymm	2	1	n/a	1	n/a	1	1
	≠ 1 st dose yyyymm		2	2	2	2	2	2
Partial: yyyy	= 1 st dose yyyy	3	1	3	1	n/a	1	1
	≠ 1 st dose yyyy		3		3	3	3	3
Missing		4	1	4	1	4	1	1

1=Impute the date of first dose; 2=Impute the first of the month; 3=Impute January 1 of the year;
4=Impute January 1 of the stop year

Note: For subjects who were never treated (first dose date is missing), partial start dates will be set to the first day of the partial month or first day of year if month is also missing.

Imputation Rules for Partial or Missing Stop Dates

Initial imputation

- If the month and year are present, impute the last day of that month.
- If only the year is present, impute December 31 of that year.
- If the stop date is entirely missing, assume the event or medication is ongoing.

If the imputed stop date is before the start date, set stop date to missing.

If the imputed stop date is after the death date, impute as death date.

Imputation Rules for Partial or Missing Death Dates

If death year and month are available but day is missing:

- If yyyyymm for the date last known to be alive equals yyyyymm for death date, set death date to the day after the date last known to be alive.
- If yyyyymm for the date last known to be alive is less than the yyyyymm for death date, set death date to the first day of the death month.

[figure not shown]
- If yyyyymm for the date last known to be alive is greater than yyyyymm for death date, assume death date is in error, do not impute and censor the subject survival time.

If month and day are missing and year of death is known:

- If yyyy for the date last known to be alive equals yyyy for death date, set death date to the day after last known to be alive date.
- If yyyy for the date last known to be alive is less than yyyy for death date, set death date to the first day of the death year.
- If yyyy for the date last known to be alive is greater than yyyy for death date, assume death date is in error, do not impute and censor the subject survival time.

If a death date is totally missing:

Do not impute and censor the subject survival time.

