- Efficacy parameters for R/R AML: response rate (response defined as CR/CRi/morphologic leukemia-free state [per modified IWG criteria] or CRh), duration of response, time to response, event-free survival and overall survival (duration of response, event-free survival, and overall survival will only be measured in the expansion cohort)
- Efficacy parameters for MRD-positive AML: response rate (response defined as conversion from MRD+ status with 0.1% threshold to MRD-), time to response,

relapse-free survival, and overall survival (relapse-free survival and overall survival will only be measured in the expansion cohort)

- Efficacy parameters for MDS: response rate (response defined as CR or marrow complete remission [per International Working Group (IWG) standardized response criteria]), duration of response, time to response, event-free survival and overall survival (duration of response, event-free survival, and overall survival will only be measured in the expansion cohort)

Exploratory Endpoints:

- Depletion of LSCs
- MRD response
- Lymphocyte counts, cluster of differentiation (CD) 33+ monocytes and T cells, as well as T cell activation (including T cell subsets). Other immune subsets may also be examined
- [REDACTED]
- [REDACTED]
- [REDACTED]
- Changes in serum cytokine levels
- Frequency and severity of cytokine release syndrome (CRS) and other AEs following [REDACTED] premedication, and alternative dose step schedules of AMG330
- [REDACTED]

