5.3 Study Dates

Informed Consent Date

The date on which the subject signs the informed consent form.

Enrollment Date

Enrollment date is defined as the date collected on the Subject Enrollment CRF page.

Study Day 1

Study Day 1 is defined as the first day that AMG 330 is administered to the subject.

Study Day

If date is on or after first administration of AMG 330: study day= (date - date of Study Day 1) + 1

If date is prior to date of first administration of AMG 330: study day= (date – date of Study Day 1)

Last Investigational Product Dose Date

The last IP dose date for each subject is defined as the end date of last infusion of AMG330.

End of Investigational Product (IP) Administration Date

End of IP Administration for each subject is defined as the date of decision was made to end IP reported on the End of IP Administration CRF page.

End of study (EOS)

End of study for an individual subject is defined as the date of the final study visit (EOS visit) when assessments and procedures are performed. The EOS visit should occur approximately 4 weeks (+ 1 week) after the last dose of AMG 330 or prior to the initiation of other AML therapy, whichever occurs earlier. Subjects who complete the EOS visit will be considered to have completed the study.

Death Date

For subjects who die during the study, the death date will be recorded on the end of study CRF in the “date subject ended study” field. Incomplete death dates where only the day of death date is missing will be imputed using the following rules:

Day 1 of the month will be used if year and month indicate that death happened in different month from last known alive date;

One day after last known alive date will be used if death happened in the same month as last known alive date.

The imputed death date will be used in calculation of duration of response, progression-free survival and overall survival.

Last Known Alive Date

For subjects not known to have died, their last date known to be alive will be determined as the latest date associated with clinic visits before data cutoff date including, for example, but not limited to the following:

- Date of Enrollment on Subject Enrollment CRF
- Date First Taken, Date Last Taken on Concomitant Medications CRF
- Date Performed on ECOG Performance Status, Vital Signs, Electrocardiogram, Procedures CRFs
- Admission Date, Discharge Date on Hospitalizations CRF
- Date of Examination on Physical Measurement CRF

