Duration of response is defined as the interval from the date of the first disease assessment indicating an overall response to the first documented relapse, disease progression, or death due to any cause, whichever occurs first. Subjects without relapse, disease progression or death until the analysis data cut-off date will be censored at the last adequate disease assessment date. Only subjects with a response will be evaluated for DOR.

DOR time in days = earlier of (date of first relapse or disease progression or death or date of censoring) – date of the first observation of overall response +1.

DOR time in months= earlier of (date of first relapse or disease progression or death or date of censoring) – (date of the first observation of overall response +1)/30.4

Overall Survival (OS)

Overall survival is defined as the time from enrollment until death due to any cause.

Subjects alive will be censored at the last known date. If the date last known to be alive is after the date that triggers the analysis (ie, the data cutoff date), the subject will be censored at the date of last contact through the analysis trigger date.

Event-free Survival:

Event-free survival (EFS) is defined as the interval from first administration of AMG 330 to the earliest of date of treatment failure, relapse for responders, or death due to any cause. Censoring is at the last evaluable post-baseline response assessment; otherwise,

at first administration of AMG330. For non-responders, the event date for treatment failure is assigned as the date of first administration of AMG 330.

Event-free Survival in days = earlier of (date of treatment failure or relapse or death or date of censoring) – date of the first administration of AMG 330 +1.

Event-free Survival in months = earlier of (date of treatment failure or relapse or death or date of censoring) – (date of the first administration of AMG 330 +1)/30.4.

Time to Response (TTR)

Time to response defined as the interval from the first administration of AMG 330 to the first documentation of response. Time to response is evaluated only for subjects who achieved a response.

Time to response is calculated as the number of days:

(date of first response – date of study day 1 +1).

6. Analysis Sets

The analysis of all endpoints, unless noted otherwise, will be conducted on the Safety analysis set defined in [Section 6.1](#).

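### SAP Appendix A censors some subjects known to have died, against the SAP's own definition of overall survival, which on average biases survival upward by about 1 to 2 points per such death

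*SAP*

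**What the plan says.** SAP Section 5.4 gives the endpoint: "Overall survival is defined as the time from enrollment until death due to any cause". It names one class of subject to be censored: "Subjects alive will be censored at the last known date".

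SAP Section 5.3 has a death-date rule, but it is limited to one case: "Incomplete death dates where only the day of death date is missing will be imputed using the following rules". The same section defines the last known alive date for a restricted group: "For subjects not known to have died, their last date known to be alive will be determined as the latest date" found across a list of CRF and laboratory dates.

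SAP Appendix A, under its rules for partial or missing death dates, goes further than Section 5.3. When only the year of death is known and it matches the last-alive year, the event is kept: "set death date to the day after last known to be alive date". The same-month case is treated in the same way. When the recorded death month or year is earlier than that of the last-alive date, the instruction in both places is to "assume death date is in error, do not impute and censor the subject survival time". When the date is wholly missing, the instruction is likewise to "do not impute and censor the subject survival time".

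On scope, SAP Section 2.1 says for each of the three indications that "overall survival will only be measured in the expansion cohort". SAP Section 9.5.2 makes Kaplan-Meier curves with 80% intervals optional.

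**The concern.** Not knowing when a subject died is different from not knowing whether the subject died. In all three censoring statements the fact of death is on record and only its date is missing or contradictory. Removing the event because the subject is dead with a poor date makes the censoring depend on the outcome, which breaks the assumption behind the Kaplan-Meier estimate.

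Three things follow:

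- The appendix and the endpoint definition cannot both be followed.
- The censoring instruction is incomplete, since no last-alive date is defined for a subject known to be dead.
- The estimate leans upward in single-arm cohorts of at most 30, where one event is visible.

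Such cases could plausibly arise. Protocol Section 8.1 allows follow-up through family, friends or other physicians, and Protocol Section 12.4 allows public-record searches for survival status in subjects who withdraw early. The documents do not say how often a death learned of in this way would lack a date.

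**Working it through.** **The plan's own figures.** The documents give no assumed median, event count or precision for OS, so there is no OS figure to reproduce. The stated expansion-cohort figures do reproduce:

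- At least one adverse event in 30 subjects: 1 − 0.9^30 = 95.8% (stated 96%) and 1 − 0.8^30 = 99.9% (stated 100%).
- Stopping after 10 subjects: 0.95^10 = 59.9% (stated above 59%) and 0.8^10 = 10.7% (stated below 11%).
- 80% Clopper-Pearson intervals: 5.5% to 45.0% for 2/10 and 10.9% to 32.5% for 6/30.

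**The rules side by side** (all for a subject recorded as dead):

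| What is known of the death date | SAP Appendix A treatment |
|---|---|
| Year and month, same as last alive | Event, day after last alive |
| Year and month, later than last alive | Event, first of that month |
| Year and month, earlier than last alive | Censored |
| Year only, same as last alive | Event, day after last alive |
| Year only, later than last alive | Event, first of that year |
| Year only, earlier than last alive | Censored |
| Nothing | Censored |

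Three of the seven rows conflict with Section 5.4.

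**Effect of one censored death, exactly.** If a death occurs with r subjects at risk, it contributes the factor (r − 1)/r. Censoring it at that point removes the factor, so every later Kaplan-Meier value is multiplied by r/(r − 1). Take 30 subjects, no other censoring, and a true 6-month OS of 50% (15 deaths):

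- Fifth death censored (r = 26): 50% × 26/25 = 52.0%.
- Tenth also censored (r = 21): 52.0% × 21/20 = 54.6%.
- Fourteenth also censored (r = 17): 54.6% × 17/16 = 58.0%.

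**Average effect, by simulation.** These inputs are assumptions, not from the documents: n = 30, exponential survival, 12 months of follow-up, last contact 0 to 1 month before death, and undated deaths picked at random among all deaths. Medians are 6 months and 10.8 months; the latter is the figure Protocol Section 2.1.2 quotes for MDS after hypomethylating-agent failure. Mean 6-month OS:

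| Median (months) | Undated deaths | True dates | SAP censoring | Event, day after last alive |
|---|---|---|---|---|
| 6 | 1 | 49.8% | 51.3% | 49.7% |
| 6 | 2 | 50.0% | 53.1% | 49.8% |
| 6 | 3 | 49.6% | 54.1% | 49.2% |
| 6 | 5 | 50.1% | 57.9% | 49.5% |
| 10.8 | 1 | 67.7% | 69.3% | 67.6% |
| 10.8 | 5 | 67.8% | 76.2% | 67.1% |

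The SAP rule adds about 1.5 points for one undated death, 3 for two, 4.5 to 5 for three, and 8 for five. Across 32,000 comparisons at 1, 3, 6, 9 and 12 months, the censored curve fell below the true-date curve in 509 (1.6%).

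**Longer gaps before death.** With one undated death and last contact spread uniformly over 0 to 1, 0 to 6 or 0 to 12 months before death, across both medians:

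| Time | SAP censoring, bias in points | Event day after last alive, bias in points |
|---|---|---|
| 6 months | about +0.9 to +1.6 | about −0.1 to −1.0 |
| 12 months | about +1.1 to +2.2 | essentially 0 |

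At 6 months with a 0 to 12 month gap and a median of 6 months, the two errors are nearly equal and opposite, at a little under 1 point each. By 12 months the imputed version has no bias in this model, because every death has by then been counted.

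**The case against.** The best defence is that the cases differ in kind. A known month or year bounds when death occurred, so imputation is anchored. A wholly missing date has no upper bound, and an inconsistent one means the record contradicts itself. The rule is also a last resort: Protocol Section 12.3 provides for consistency checks and site queries, and the formal analyses use a locked database. Imputing the day after last contact uses the earliest possible date, so it pulls the curve down at interim times when contact was lost long before death. The shift is also small beside the sampling error: at n = 30 and 50% survival the 80% half-width is about 1.28 × √(0.25/30) = 11.7 points.

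Much of that stands as a limit on size and on how the fix should be described. It does not rescue the rule. An uncertain date is a reason to impute and show sensitivity, not to discard a known event. The imputation is as good or better in every setting checked except the longest gaps, where the two are about level at 6 months and imputation is better at 12.

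A reader might infer stronger claims that the documents do not support:

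- **That the rule can only raise OS.** With one undated death, the censored curve lay below the true curve at 6 months in about 1% to 28% of simulated cohorts, rising with the gap before death. The bias is upward on average.
- **That each such death costs 3.3 points (1/30).** That is the effect immediately after a very early death; the average at 6 months is about half of it or less.
- **That these subjects count as survivors to data cutoff.** They are censored, not carried forward alive.
- **That any death date before the last-alive date triggers censoring.** The rule is written for partial dates only; Appendix A is silent on a complete but inconsistent date.

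**Conclusion.** The point holds as an internal contradiction with a predictable average direction. Three statements in SAP Appendix A censor subjects recorded as dead, Section 5.4 does not allow this, and the date at which to censor them is undefined. Expect an upward bias of roughly 1 to 2 percentage points per undated death in a 30-subject expansion cohort. That range rests on assumed exponential survival with medians of 6 to 10.8 months, 12 months of follow-up, and last contact up to 12 months before death.

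The number of undated deaths is not given in the documents. If there are none, the effect is zero.

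A reader might infer that dose or safety conclusions are at risk. They are not: DLTs, the MTD and the decision to extend the expansion cohort do not use OS, and Protocol Section 10.4.3.2 treats the efficacy analyses as exploratory. This is a low-severity correction, best made before database lock so that the handling of any such death is not chosen with the data in view.

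**What to change.** In SAP Appendix A, replace all three censoring statements with one rule. If death is confirmed but its date is missing or inconsistent after a site query, count the death as an OS event dated the day after the last known alive date. Apply the same rule to a complete death date that precedes the last-alive date, which is currently uncovered.

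In SAP Section 5.3, extend the last known alive date to these subjects. For them, use only dates that show the subject alive: the current source list includes the end-of-study date and event dates tied to death, which for a known death may be the disputed date itself.

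List every imputed case with its last-alive date, and show the version with these subjects censored at that date as a sensitivity analysis.

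The cost is a few lines of SAP text, one listing and one extra run, with no new data collection. The downside should be stated in the SAP: the imputed date is the earliest possible, so OS at interim time points may be slightly underestimated when last contact was long before death.
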